The lead safety endpoint adverse event is symptomatic intracranial hemorrhage (SICH), defined using the SWIFT PRIME trial criteria⁵⁵: an increase of 4 or more points on the NIHSS within 24 hours of stimulation associated with parenchymal hematoma type 1 (PH1), parenchymal hematoma type 2 (PH2), remote intraparenchymal hemorrhage (RIH), subarachnoid hemorrhage (SAH), or intraventricular hemorrhage (IVH). In addition, all hemorrhages, both symptomatic and asymptomatic, will also be separately classified and analyzed by radiologic subtype, as hemorrhagic infarction type 1 (HI1), hemorrhagic infarction type 2 (HI2), PH1, PH2, RIH, SAH, or IVH.⁵⁵ A central neuroimaging core lab, blinded to treatment assignment, will review all brain MRI scans obtained at 24h and rate presence and type of radiologic hemorrhagic transformation. In addition, in patients who experienced worsening by 4 or more NIHSS points in the first 24 hours, they will review any and all additional brain MRI or CT scans obtained during the 24h time period,

SICH is the primary safety endpoint of the current trial, but trial results will be assessed on a variety of additional safety, feasibility, and tolerability results as well. It is anticipated that, after completion of the current trial, the judgement of whether to proceed directly to a pivotal trial, to proceed to a larger safety and preliminary efficacy trial, or to not proceed with further development, will rest on a considered and informed assessment of all outcome measures. It is important therefore to collect data on a wide range of safety

endpoints and a wide range of measures of functional outcome, as is planned in this proposal. In making the selection of a primary safety endpoint, an emphasis was placed on ensuring patient safety throughout the course of the trial by choosing an endpoint with uncontested clinical relevance (Symptomatic Intracranial Hemorrhage).

D.6.10.3 Additional Adverse Events with Specific Interrogation

In addition to general screening for all serious adverse events and focused elicitation of symptomatic intracranial hemorrhage events, the following events will be specifically interrogated for and recorded in the case report forms: skin redness, scalp rash, hair loss, seizure, headache, sensitivity to light, new ischemic stroke, deep venous thrombosis, pulmonary embolism, pneumonia, acute MI.

E. Safety Monitoring

E.1. Data and Safety Monitoring Plan

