The trial will be monitored by an Independent Data and Safety Monitoring Board (DSMB). [name] from department of neurorehabilitation will lead the DSMB. DSMB will assess for the causal relationship of the serious adverse event to the study treatment as definite, probable, possible, unlikely, or unrelated.

DSMB will meet at the completion of each dose tier, review all safety data, and determine whether the study will proceed to the next dose tier. DSMB deliberations will be guided by: 1) a formal stopping/escalation rule, based on the occurrence of the lead safety endpoint, symptomatic intracranial hemorrhage (SICH), and 2) The DSMB members' clinical judgement upon review of all other safety outcomes. In addition, DSMB will monitor separately the patients who enroll in the study with a stroke scale 0-3 during the study as they are treated to determine if they have an increase in NIHSS of 2 or more or which is disabling.

Furthermore, Food and Drug Administration (FDA) will be notified if there is one occurrence of SICH prior to repeating the tier or escalating to a higher tier.

E. 2. Statistical Design and Analyses Plan

E.2.1. Sample size

The study sample size derives from the use of the 3+3, rule-based, modified Fibonacci, dose escalation design, with 3:1 randomization to active treatment vs sham control. There will be 6 dose tiers, reflecting increasing intensity and duration of stimulation (Figure 7). The 3+3 study design (3 patients and 1 sham) with 6 dose tiers yields a sample size of at least 24 and potentially up to 48. The 3+3 design is the classical approach to dose escalation in first-in-human studies.^{57,58} While newer, adaptive designs for dose escalation trials have been developed, they are more complex and have limited advantages when major toxicities are not expected.⁵⁹ Therefore, the rule-based, 3+3 design remains the dominantly employed approach in current dose-escalation studies. We will take every step to avoid missing data by scheduling of the follow-up visits early in visit time windows and readiness to travel to the patient's location to perform needed assessments. Should any missing data occur, primary analyses will be performed using multiple imputation, with sensitivity analyses including complete case and worst possible outcome analyses.⁶⁰

E.2.2. Baseline characteristics

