The demographic and baseline clinical characteristics of the study population will be delineated with standard descriptive statistics. Categorical variables describing the clinical history, examination findings, and initial treatment will be summarized by

frequencies. Continuous variables such as vital signs, laboratory results, and time variables will be characterized by means, standard deviations, and 95% confidence intervals (CI). Ordinal and non-normally distributed variables (such as the NIHSS) will be characterized by medians and interquartile ranges. Baseline characteristics will be compared between the tDCS stimulation group with sham group to assess covariate balance. Wilcoxon Rank-Sum tests will be used for continuous or ordinal variables; Fisher's exact tests and chi-square tests will be used for grouped or nominal categorical variables.

E.2.3. Safety and Tolerability (Specific Aim 1)

E.2.3.1 Dose Escalation

The study Data and Safety Monitoring Board (DSMB) will meet at the completion of each dose tier, review all safety data, and determine whether the study will proceed to the next dose tier. DSMB deliberations will be guided by: 1) a formal stopping/escalation rule, based on the occurrence of the lead safety endpoint, symptomatic intracranial hemorrhage (SICH), and 2) The DSMB members' clinical judgement upon review of all other safety outcomes. The formal dose escalation rule uses SICH frequency to gate the occurrence and pace of escalation through the 6 dose tiers. If no SICH occurs in the 3 active patients at a dose tier, enrollment may escalate to the next dose tier. If one SICH occurs, 3 more active (and 1 more control) patient will be enrolled at that dose tier before escalation. If 2 SICHs occur at a dose tier, further study enrollment is held until detailed review by the DSMB (Fig 6). In addition, whenever the formal SICH criteria for dose escalation has been met, the DSMB will formally meet, review the SICH data and all other safety data, and advice regarding proceeding to the next tier, continuing at the current tier, or placing the study on hold.

E.2.3.2. Primary Safety Endpoint Analysis

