For the final statistical analysis of the primary SICH safety endpoint, a chi-square test will be used to detect differences in the rate of SICH between the active treatment and sham patients and higher and lower dose tiers. The treatment will be considered to have exhibited adequate safety in the current trial to proceed to future, larger, pivotal efficacy trials if tDCS results in lower or equivalent rates of SICH compared to sham.

E.2.3.3. Secondary Safety Endpoints Analysis

In secondary safety endpoint analyses, the following will be compared between the active treatment and sham patients, and between higher and lower dose tiers, using chi-squared tests: **1) Asymptomatic ICH by 24h** (intracranial hemorrhage not associated with NIHSS worsening ≥ 4); **2) Early neurologic deterioration** (worsening ≥ 4 on NIHSS during the 24-hour period after stimulation, with or without intracranial hemorrhage); **3) All-cause mortality at day 90 (mRS);** and **4) All serious adverse events.**

E.3.3. Tolerability Endpoint Analysis

The lead tolerability endpoint is completion of the protocol-assigned stimulation treatment without early cessation due to cutaneous, neurologic, nociceptive or other adverse effects. Experience with tDCS in post-stroke patients indicates only infrequent cutaneous (itching, tingling) adverse effects are likely to occur. Accordingly, for the current study, a patient will be considered to have tolerated the procedure if at least 75% of the stimulus period was completed. The treatment will be considered generally tolerable if, among all enrolled patients, tolerated procedures are achieved in $\geq 90\%$ of patients, assessed with a one-sided p value of 0.025. Secondary tolerability endpoints will be the

rate and severity of cutaneous, neurological, and pain items of the technician-filled (Figure 7) and patient-filled tolerability forms ⁴⁹, descriptively compared between active treatment and sham patients, and between higher and lower dose tiers.

E.3.4. Feasibility Endpoint Analysis (Specific Aim 2)

A time-motion analysis and mock run-throughs will be conducted prior to first enrollment. Nonetheless, it is anticipated that processes to optimize rapid placement of the cap and electrodes will continue to improve with experience gained from initially enrolled patients. The predefined success threshold for feasibility will be median time from randomization to tDCS initiation \leq 10 minutes in the last 10 enrolled patients.

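### E.2.3.2: in a trial that clears all six tiers by the 3+3 rule, the SICH chi-square test can show benefit but not harm, and the adequacy criterion has no margin and can be read two ways

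*Combined protocol and SAP*

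**What the plan says.** Section E.2.3.2 states that "a chi-square test will be used to detect differences in the rate of SICH between the active treatment and sham patients", and also between higher and lower dose tiers. It gives no significance level or sidedness and does not define the tier split. It then sets a criterion: safety is adequate to move to larger, pivotal trials "if tDCS results in lower or equivalent rates of SICH compared to sham". *Equivalent* is not defined there or elsewhere. The only significance level in the plan is for tolerability (E.3.3), "assessed with a one-sided p value of 0.025".

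The data reaching this test are shaped by E.2.3.1. A tier clears with no SICH in its three active patients. The expansion rule reads: "If one SICH occurs, 3 more active (and 1 more control) patient will be enrolled at that dose tier before escalation". A separate hold rule then caps the events that a cleared tier can contain: "If 2 SICHs occur at a dose tier, further study enrollment is held until detailed review by the DSMB". Section E.2.1 says that the design "yields a sample size of at least 24 and potentially up to 48".

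Two other passages bear on the weight of the criterion. Section D.6.10.2 says that the choice of next step "will rest on a considered and informed assessment of all outcome measures". Section E.1 has the DSMB review every tier, and the FDA is notified "if there is one occurrence of SICH prior to repeating the tier or escalating to a higher tier".

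**The concern.** The 3+3 rule limits how many active SICHs a completed trial can contain. A significance test applied afterwards sees only what the rule let through, with 6 to 12 sham patients as the comparator. The question is whether the test can find harm in such data, and what the criterion decides if it cannot.

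At stake is the trial's stated conclusion on its primary endpoint. A completed trial could be declared adequately safe automatically, or could pass or fail on whether one or two sham patients bleed. Because the plan does not say which reading applies, the choice could be made after the results are known. Section E.3.5 calls the efficacy analyses exploratory and descriptive for lack of power. The SICH comparison carries no such caveat and has a pass criterion attached.

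**Working it through.** **Inputs.** Six tiers, 3 active and 1 sham per cohort (E.2.1). A tier clears at 0/3 or 1/6 active and is held at two SICHs (E.2.3.1). Assumptions: two-sided 0.05, because no alpha is stated for SICH; only active SICHs trigger expansion or hold; the SICH rates used below, because the available text gives none.

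**The plan's own figure.** 6 × (3+1) = 24 and 6 × (6+2) = 48. The stated range is reproduced.

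**Possible data.** If k tiers expand and all six clear, there are exactly k active SICHs in 18+3k active patients, against s SICHs in 6+k sham patients (k = 0 to 6).

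**Active v sham, direction of harm.** The case most favourable to showing harm is s = 0. With N = 24+4k and 3:1 allocation, Pearson chi-square without correction reduces to N·k / [3(N−k)].

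| k | Active v sham | Chi-square | Two-sided p |
|---|---|---|---|
| 0 | 0/18 v 0/6 | undefined | – |
| 1 | 1/21 v 0/7 | 28×1/(3×27) = 0.346 | 0.557 |
| 2 | 2/24 v 0/8 | 0.711 | 0.399 |
| 3 | 3/27 v 0/9 | 1.091 | 0.296 |
| 4 | 4/30 v 0/10 | 1.481 | 0.224 |
| 5 | 5/33 v 0/11 | 1.880 | 0.170 |
| 6 | 6/36 v 0/12 | 48×6/(3×42) = 2.286 | 0.131 |

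The one-sided p at k = 6 is 0.065, so the tolerability level of 0.025 is not reached either. The likelihood-ratio form gives 0.053 two-sided (0.027 one-sided) and Fisher's exact test 0.31. Any sham SICH weakens the evidence of harm.

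**Direction of benefit.** For 0/18 v 2/6, chi-square is 24×(18×2)²/(18×6×2×22) = 6.545, p = 0.011. The test can reach significance in favour of tDCS.

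**Higher v lower tiers.** Over every cut between consecutive tiers, the smallest p is for tier 6 (1/6) v tiers 1-5 (0/15): 21×15²/(6×15×1×20) = 2.625, p = 0.105. This bound needs the assumption that only active SICHs trigger expansion. If sham SICHs also did, lower tiers could show 0/6 active. Three such tiers give 1/6 v 0/24: 30×24²/(6×24×1×29) = 4.14, p = 0.042. The active v sham minimum of 0.13 is the same on either reading.

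**Reading 1 of the criterion: not significantly different.** No table above is significant for harm, so no such trial can fail.

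**Reading 2: observed active rate no higher than sham.** Since k/(18+3k) = (k/3)/(6+k), a trial passes only if s ≥ k/3. With k = 0 it always passes, k = 1-3 needs one sham SICH, and k = 4-6 needs two. So 1/21 v 0/7 fails and 1/21 v 1/7 passes.

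**How often.** With active rate p, a tier clears with probability c = (1−p)³ + 3p(1−p)⁵, and six clear with c⁶. Given completion, k is binomial(6, e) with e = 3p(1−p)⁵/c, and sham SICHs are binomial in 6+k.

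- Equal 5%: c = 0.8574 + 0.1161 = 0.9734 and c⁶ = 0.85. Failures given completion are 0.379×0.95⁷ (k = 1) + 0.128×0.95⁸ (k = 2) + 0.023×0.95⁹ (k = 3) + about 0.002 (k = 4 and above) = 0.37.
- Equal 1% and 2%: 15% and 25% of completed trials fail.
- No SICH in either arm, so no test: 79%, 63% and 34% of completed trials at equal 1%, 2% and 5%.
- 10% v 5%: c = 0.729 + 0.177 = 0.906, so 55% complete; half of those pass.
- If sham SICHs also count toward expansion and hold, completion at 10% v 5% falls to 46% and passing to 40%.

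**The case against.** The strongest reply is that E.2.3.2 is not the only gate. The 3+3 rule, DSMB review after each tier and FDA notification protect participants, and D.6.10.2 rests the next step on all outcomes. Low power is inherent in a 24-48 patient escalation study. All of this stands, and it limits the point to the wording of one conclusion. It does not define *equivalent* or withdraw the criterion, which remains a stated condition for moving to pivotal trials.

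A reader might infer three stronger claims that the documents do not support.

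- *That participants are unprotected.* The escalation rule and the DSMB act independently of this test, and the DSMB may hold a tier even when the SICH rule is met.
- *That the test can never be significant.* It can favour tDCS, as shown above. It can also show harm if a two-SICH hold is lifted and enrollment continues: 10/36 v 0/12 gives p = 0.040. The finding covers only trials that clear all six tiers with no hold lifted.
- *That this criterion alone sends tDCS to a pivotal trial.* D.6.10.2 says otherwise.

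It is also fair that the percentages depend on assumed rates and on an unstated point: the one-SICH and two-SICH sentences in E.2.3.1 do not say whether a sham SICH counts.

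**Conclusion.** The point holds within its scope, and the plan should be amended. In a trial that completes by rule, the chi-square test cannot show that tDCS increases SICH: the smallest Pearson p in that direction is 0.13, and it is 0.56 at 1/21 v 0/7. This rests on an assumed two-sided 0.05, but the plan's only stated level is missed too. The criterion then either cannot fail or fails 15%, 25% and 37% of completed trials at assumed equal true rates of 1%, 2% and 5%. The tables and p-values follow from the plan's rules; these percentages also need the assumed rates and the active-only reading of the escalation rule. The consequence is confined to the stated conclusion on the primary safety endpoint.

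**What to change.** 1. In E.2.3.2, and for the same comparisons in E.2.3.3, label active v sham and higher v lower tier comparisons descriptive, as E.3.5 does for efficacy. Define the tier split. Report counts with exact confidence intervals per arm and for the difference.
2. Delete the comparison with sham as the adequacy criterion. State instead that the SICH conclusion is the outcome of the 3+3 rule and DSMB review, reported with the pooled active SICH rate and its exact one-sided 95% upper limit, as one part of the overall judgement in D.6.10.2. That limit is 15.3% for 0/18, 20.7% for 1/21 and 30.3% for 6/36.
3. State the limit's weaknesses. It pools six dose tiers, and its 95% coverage does not hold conditional on completing the 3+3 rule. Since 15.3% is the lowest limit a completed trial can give, it never misses a true rate up to that value. Above it, the miss rate can far exceed 5%: about 46% at a true rate of 21% (k = 0 or 1: 0.137 + 0.323) and 75% at 25%. Any ceiling is for the sponsor and DSMB to set in advance.
4. Reword Hypothesis I-a, which predicts no increase in SICH risk, as estimation. It would also help to state in E.2.3.1 whether a sham SICH counts.

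Adding a margin instead would not rescue the test. On assumed equal rates, one-sided 0.025 and 80% power, a 10-point margin needs 21 sham patients at 2% and 50 at 5%, against 6-12 available.

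The cost is a text amendment with prior IRB approval, and no extra patients, visits or data. The downside is candour: the trial says that it bounds the active SICH rate only to about 15-30% and cannot establish equivalence to sham.

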Hypothesis I-a: tDCS will be safe in AIS patients with no increased risk of symptomatic intracranial hemorrhage (SICH) within the 24-hour period after stimulation. Hypothesis I-b: tDCS will not increase the rates of asymptomatic intracranial hemorrhage, early neurological deterioration (NIHSS during the 24-hour period after stimulation), 90-day mortality, and all serious adverse events. Hypothesis I-c: Majority of AIS patients ($\geq 90\%$) will tolerate the tDCS by completing at least 75% of the stimulation period with no major stimulation related pain, discomfort and skin changes.

Specific Aim II: To determine the feasibility of delivering tDCS in AIS.

Hypothesis II-a: tDCS will be started more rapidly over the course of the study and in the last 10 patients median time from randomization to tDCS initiation will be ≤ 10 minutes.

Specific Aim III: To explore the potential imaging and clinical efficacy of tDCS in AIS.

This aim will be accomplished by measuring, in actively treated and sham patients:

- 1) Early and late penumbral salvage, defined as proportion of penumbral tissue on baseline multimodal MRI that does not proceed to infarct on 2-hour and 24-hour MRI (PWI);
- 2) Early and

late collateral enhancement, evidenced by reduced perfusion lesion volume on 2-hour and 24-hour perfusion-weighted MRI (PWI); **3)** Early and late reduction in infarct growth from baseline to 2-hour and 24-hour MRI; **4)** Early improvement in neurologic deficit (NIHSS at 24h); **5)** Improvement in final 3-month disability and quality of life (modified Rankin scale, AMC Linear Disability Scale, EQ-5D, and Barthel Index)

Impact

This in-hospital safety trial, in non-thrombectomy candidates in a closely-observed, Emergency Department and hospital settings, will identify tDCS dose regimens that are feasible, well-tolerated, and preliminarily safe in patients with acute ischemic stroke. Study finding will identify the most promising dose regimens to advance to phase 2b and pivotal phase 3 efficacy trials for two patient populations with pressing need for improved therapies: 1) thrombectomy ineligible patients (standalone neuroprotection), and 2) thrombectomy-eligible patients (bridging neuroprotection in prehospital and early ED-arriving patients).

B. Background and Significance

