E.3.5. Exploratory Efficacy Endpoints Analysis (Specific Aim 3)

E.3.5.1. Exploratory Imaging Biomarker Efficacy Endpoints

This study is underpowered to definitively determine efficacy, so all imaging efficacy analyses will be purely exploratory and descriptive. Imaging biomarker efficacy endpoints will be characterized in the active and sham patients, and in higher and lower dose tiers, using means and 95% confidence intervals. The six imaging efficacy endpoints of greatest interest that will be explored are: early and late penumbral salvage, early and late collateral flow enhancement, and early and late infarct growth.

E.3.5.2. Exploratory Clinical Efficacy Endpoints

This study is underpowered to definitively determine efficacy, so all clinical efficacy analyses will be purely exploratory and descriptive. Four clinical outcome measures were selected based on their reliability, familiarity to the neurologic community, and adaptability for use in patients who have had a stroke. These endpoints are: the modified Rankin Scale (mRS), a rating of global disability; the Barthel Index (BI), a measure of instrumental activities of daily living; the National Institutes of Health Stroke Scale (NIHSS), a measure of neurologic deficit severity; and the EuroQol (EQ-5D), an assessment of health-related quality of life; and AMC Linear Disability Scale, a granular degree of disability.

Clinical efficacy endpoints will be characterized in the active and sham patients, and in higher and lower dose tiers. Early course clinical efficacy endpoints of greatest interest that will be explored are: **1)** Normalized change in neurologic deficit from baseline to 24h (normalized delta NIHSS – linear variable, analyzed with means and 95% CIs; and **2)** Degree of neurologic deficit at 24h (NIHSS – quasi-linear variable, analyzed with means and 95% CIs). Final outcome clinical efficacy endpoints of greatest interest that will be explored are: **1)** Degree of disability at 90 days, assessed across all 7 levels of the modified Rankin Scale – ordinal variable, analyzed with medians (IQRs) and means (95% CIs); **2)** Functional independence (mRS 0-2) at 90 days – binary variable, analyzed with rates and 95% CIs; **3)** Granular degree of disability at 90 days (AMC Linear Disability Scale) – linear variable, analyzed with means and 95% CIs; and **4)** Health-related quality of life (EQ-5D) – linear variable, analyzed with means and 95% CIs.

References:

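### E.2.3.3 tests four secondary safety endpoints by chi-squared with only 6 to 12 sham patients; the test is unreliable at these counts, can barely show harm, and cannot support Hypothesis I-b

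*Combined protocol and SAP*

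**What the plan says.** E.2.3.3 names four secondary safety endpoints: asymptomatic ICH by 24 hours, early neurologic deterioration, death by day 90, and all serious adverse events. It says "the following will be compared between the active treatment and sham patients, and between higher and lower dose tiers, using chi-squared tests". That is four endpoints in two contrasts, or eight tests. The section states no significance level or sidedness, does not say whether a continuity correction applies, and does not define where lower tiers end and higher tiers begin.

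These tests serve Hypothesis I-b in the Specific Aims, which begins "tDCS will not increase the rates of asymptomatic intracranial hemorrhage, early neurological deterioration" and goes on to 90-day mortality and serious adverse events.

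On size, E.2.1 says the 3+3 design "with 6 dose tiers yields a sample size of at least 24 and potentially up to 48", "with 3:1 randomization to active treatment vs sham control".

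Three other places bear on the point:
- E.2.2, for baseline comparisons, says "Fisher's exact tests and chi-square tests will be used for grouped or nominal categorical variables", so an exact test is already in the plan.
- E.3.3 gives the plan's only significance level, for tolerability: "assessed with a one-sided p value of 0.025".
- E.3.5.2 says "all clinical efficacy analyses will be purely exploratory and descriptive", on the ground that the study is underpowered for efficacy. E.2.3.3 has no such label.

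**The concern.** The chi-squared approximation needs reasonable expected counts. With six sham patients and uncommon events it does not have them. The 3:1 allocation also makes the test behave differently in the two directions: a couple of chance events in the small sham arm can cross 0.05, while an excess on tDCS must be very large to do so.

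Two misreadings are then possible. A chance cluster in about six sham patients could be reported as significantly fewer bleeds, deteriorations or deaths on tDCS. More seriously, a non-significant result could be taken as support for Hypothesis I-b when the test had almost no ability to detect an increase.

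**Working it through.** **Inputs from the documents.** Six tiers of 3 active and 1 sham give 6 × (3+1) = 24. If every tier is expanded, 6 × (6+2) = 48. Both match E.2.1. The arms are therefore 18 v 6 at the minimum and 36 v 12 at the maximum.

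**Assumptions, because the plan gives no value.** Two-sided 0.05 per test; uncorrected Pearson unless stated otherwise; a range of event rates; tiers 1–3 v 4–6 (9 v 9 active) for the tier contrast. Arm sizes are treated as fixed.

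**Formula.** With a events in n1 active patients, b in n2 sham patients, N = n1 + n2 and t = a + b:

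X² = N·D² / [n1·n2·t·(N − t)], where D = |a(n2 − b) − b(n1 − a)|. Yates replaces D by D − N/2. Reject if X² > 3.841.

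**Single tables at 18 v 6.**
- 0/18 v 2/6: the expected sham count is 6 × 2/24 = 0.5. D = 36 and X² = 24 × 1296/4752 = 6.545, p = 0.011. Yates: D = 24, X² = 2.909, p = 0.088. Fisher: 15/276 = 0.054.
- 7/18 v 0/6: D = 42, X² = 24 × 1764/12852 = 3.294, p = 0.070.
- 8/18 v 0/6: D = 48, X² = 24 × 2304/13824 = 4.000, p = 0.0455. Yates: D = 36, X² = 2.25, p = 0.134.

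So under uncorrected Pearson two sham events against none on tDCS are enough for a nominal benefit, while harm against an event-free sham arm needs 8 of 18.

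**Direction of false positives.** Sum Bin(a; 18, p) × Bin(b; 6, p) over the rejecting tables, by direction, for one active-v-sham test:

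| True rate, both arms | Favours tDCS | Shows harm |
|---|---|---|
| 10% | 2.67% | 0.01% |
| 20% | 3.92% | 0.43% |
| 30% | 3.95% | 1.70% |
| 50% | 2.68% | 2.68% |
| 60% | 2.5% | 3.3% |

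**Power to show harm.** The same sum with different rates in the two arms (sham → active): 10% → 20% is flagged as harm in 0.9% of trials, and 20% → 40% in 12%. With Fisher the second figure is about 3.6%. Running the same sum at 36 v 12 with Pearson gives 5.0% and 24%, so the largest possible trial does not cure the problem.

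**At least one p < 0.05 over all eight tests, no true effect, N = 24.** The nominal reference for eight independent tests is 1 − 0.95⁸ = 33.7%. Enumeration and simulation give the following (rates in the order asymptomatic ICH / deterioration / death / SAE):
- Pearson, 10/10/10/20%: 16.9% with independent endpoints, 15.7% at latent correlation 0.5.
- Pearson, 30/30/30/50%: 36.6%, or about 34% at correlation 0.5.
- Pearson, 5/5/5/10%: about 6–8%.
- Yates or Fisher, across these rates: about 1–14%.

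**The case against.** The strongest reply is that little hangs on these tests. The E.2.3.2 criterion for adequate safety uses SICH alone. Escalation uses SICH counts and the DSMB's clinical judgement. D.6.10.2 leaves further development to an overall judgement of all outcomes, with no p-value rule. SICH is named as primary and these four endpoints as secondary, so a hierarchy exists at that level. Unadjusted safety comparisons are also a defensible choice in a small first-in-human study, since adjustment would make harm harder to see. All of this stands, and it limits the consequence.

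Three stronger readings are tempting and should not be made.
- A reader might infer that the plan carries a 16–37% chance of a false safety finding. That range needs a 0.05 level, an uncorrected statistic, a 9 v 9 tier split and event rates of 10–30% (SAEs 20–50%), none of which the documents give. With rare events or another test variant it is far lower.
- A reader might infer that the tests are generally tilted toward tDCS. The tilt is strong for uncommon events, vanishes at a 50% rate and reverses at 60%. It does not apply to the tier contrast.
- A reader might infer that the missing alpha, order or label is itself the error. It leaves interpretation open, but it does not create the error rates.

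It is also fair to say that Hypothesis I-b claims no increase rather than a reduction, so a chance apparent benefit would not change the answer to it. That moves the weight of the point to the low power for harm, which none of these replies addresses.

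**Conclusion.** The point holds as a poor choice of analysis for the data and the hypothesis. The chi-squared approximation is unreliable with 6 to 12 sham patients: the same 0/18 v 2/6 table gives p = 0.011, 0.088 or 0.054 depending on a variant the plan does not name. Under uncorrected Pearson at 18 v 6, a doubling of a 10% or 20% event rate is detected in only about 1% or 12% of trials, so non-significance cannot support Hypothesis I-b.

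These figures rest on an assumed two-sided 0.05 level and assumed event rates. The single-table p-values need neither an event rate nor a tier split. The eight-test error rate is a secondary and conditional matter. A change is worth making because it is cheap and closes off both misreadings; it does not bear on patient safety during the trial.

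**What to change.** In E.2.3.3, replace the chi-squared tests by event counts and rates for each arm and tier, together with the active-minus-sham risk difference and an exact 95% confidence interval. Name the interval method and define the higher/lower tier split. State that these comparisons are descriptive, as E.3.5 already does for efficacy, and that Hypothesis I-b will be judged on the interval and not on the absence of a significant p-value.

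If p-values are kept, use Fisher's exact test, which E.2.2 already names, and report them as nominal and unadjusted. Do not add a multiplicity penalty.

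The cost is a few sentences and a few lines of code; no patient, visit or dose is affected. The intervals will be wide: with 0/6 on sham, the exact upper 95% limit for the sham rate alone is 1 − 0.025^(1/6) = 46%. The sponsor also gives up nominally significant safety statements. Fisher is more conservative than Pearson for harm (about 3.6% v 12% for 20% → 40% at 18 v 6), which is why the interval should carry the harm assessment.
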